- Mean number of adenomas per colonoscopy
- Mean number of sessile serrated adenomas per colonoscopy
- Adenomas per positive colonoscopy
- Sessile serrated adenomas per positive colonoscopy
- Colonoscope withdrawal time
- Differences if quality of colon preparation
- Major complication rates (perforation, major bleeding causing transfusion)

7) Procedures Involved

Our proposed study is a randomized control trial in which patients are randomized in a single-blinded fashion into one of 2 study arms. One arm of subjects will undergo their screening colonoscopy without any colonoscope attachments (conventional). A second arm of subjects will undergo their screening colonoscopy with the Endocuff Vision attachment.

All methods (colonoscopy without any attachment and colonoscopy with Endocuff Vision attachment) are approved standard of care options, and are already in clinical use.

Data that will be reviewed as part of the study includes: age, gender, smoking status, alcohol consumption, body mass index (BMI), history of diabetes, quality of bowel prep, withdrawal time, the number of polyps, location of polyps removed, size of the polyps removed, and histopathology of the polyps. These are data points that are routinely collected and reported as part of regular care of patients. This data will be reviewed and entered into the REDCap database by medical students, residents or fellows. GI faculty members' role will be to obtain consent, perform procedures, and analysis of the de-identified data.

8) Data and/or Specimen Management and Confidentiality

Data will be accessed from patient records using an encrypted, password-protected computer at UC Davis Medical Center. The computer is stored in the GI office in PSSB building. This room is accessible by staff/faculty members of the UC Davis Gastroenterology department. Each study patient will be assigned a unique study number. Patient identifier, including patient name (First and Last) and medical record number (MRN) associated with the study number will be entered into password protected REDCap along with other aforementioned data. The principal investigators will not have access to the REDCap database, and research staff responsible for data entry will export de-identified data and distribute de-identified data to the investigators conducting data analysis.

As staff of UC Davis, each investigator will have completed HIPAA compliance training.

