The data collected will be analyzed using a one-way ANOVA. Using a baseline incidence of sessile serrated adenoma detection rate of 10%, and to detect an effect size of 50%, with a power of 0.809, we would need 687 subjects in each study arm. We therefore aimed to enroll 687 subjects into each arm (2 arms for a total of 1374 subjects) to ensure we have enough subjects in each arm to detect an effect if present.

9) Data and/or Specimen Banking

Linkage between patient identifiers(First Name, Last Name, and MRN) and study number including other data will be saved on the UC Davis REDcap database using an encrypted, password-protected computer at UC Davis Medical Center, division of Gastroenterology office located at [name] and Ticon I. Only study staff designated for data entry will have access to the REDCap database. Upon request, the de-identified data will be exported from the REDCap database and distributed to the investigators for analysis. De-identified data used for this study will not be banked for future use. At the completion of the study, all linkage between the patient identifiers and the study number will be destroyed.

10) Provisions to Monitor the Data to Ensure the Safety of Subjects

This research does not involve more than minimal risk to the subject.

The PI affirms to uphold the principle of the subject's right to protection against invasion of privacy. Throughout this study, a subject's source data will only be linked to the study database or documentation via a unique identification number. As permitted by all applicable laws and regulations, limited subject attributes, such as sex, age, or date of birth, and subject initials may be used to verify the subject and accuracy of subject's unique identification number.

11) Withdrawal of Subjects

Participation in the study is completely voluntary, thus patients can withdraw at any time during or after the procedure. Written consent will be obtained from all subjects.

Withdrawning from the procedure has no negative implication on their colon cancer screening and subsequent clinical care. If a subject desires to withdraw from the study, all information associated with the particular subject will be discarded immediately.

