A patient may also be withdrawn from the research at the discretion of the endoscopist or PI. The PI may withdraw a subject if there is a clinical suspicion for hereditary polyposis syndrome and/or new case of inflammatory bowel disease (IBD) based on the colonoscopy. Also, there are scenarios where the regular colonoscope is switched to a pediatric colonoscope. This occurs in patients with altered/ post-surgical anatomy, preventing completion of the procedure using a standard colonoscope. In these cases, subjects may be withdrawn from the study.

12) Risks to Subjects

The attachment device proposed in our study is currently FDA approved for use in colonoscopy. There is no added risk to participating subjects. There is an overall minimal risk to subjects and that risk is similar to any and all risks for conventional colonoscopy. Although we will make every effort to ensure that all patient health information remains confidential, there is the risk of loss of confidentiality.

PROTOCOL TITLE: Use of a Distal Colonoscope Attachment to Increase Detection of Sessile Serrated Adenomas

13) Potential Benefits to Subjects

Subjects may benefit from increased sessile serrated adenoma detection.

14) Multi-Site Research

Only UC Davis Medical Center Endoscopy suites will be involved in this study.

15) Community-Based Participatory Research

Not applicable

16) Sharing of Results with Subjects

Under current standard of practice, patients are contacted by the endoscopist either through the phone, mail, my chart or in person during a clinic visit to discuss endoscopic and pathology results. The results of the study will not be shared with subjects until the study has been completed and all of the data has been analyzed.

17) Prior Approvals

Not applicable

18) Provisions to Protect the Privacy Interests of Subjects

The only people that will have access to subject personal information are the principal investigators, sub-investigators and research personnel during the study period. All information collected (including age, gender, smoking status, alcohol consumption, BMI, diabetes status, withdrawal time, bowel prep quality, size, number and types of polyps removed, cecum intubation time and complications of procedure) will be de-identified.

19) Compensation for Research-Related Injury

No compensation will be provided.

20) Economic Burden to Subjects

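### Section 11 lets randomised subjects be withdrawn after the colonoscopy, at open discretion or partly for its findings, and discards data on request; if they leave the analysis, SSADR may be biased

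*Protocol*

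**What the plan says.** Protocol Section 11 (Withdrawal of Subjects) describes four ways out of the study.

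- **(a) Discretion.** "A patient may also be withdrawn from the research at the discretion of the endoscopist or PI". No criteria and no latest time are given.
- **(b) Findings.** The PI may withdraw a subject for "clinical suspicion for hereditary polyposis syndrome and/or new case of inflammatory bowel disease (IBD) based on the colonoscopy".
- **(c) Change of scope.** Where altered or post-surgical anatomy leads to a switch to a pediatric colonoscope: "In these cases, subjects may be withdrawn from the study".
- **(d) The subject's own request.** Section 11 says that "patients can withdraw at any time during or after the procedure", and that on such a request "all information associated with the particular subject will be discarded immediately".

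Discarding is stated only for (d). For (a) to (c) the protocol says neither that the data are kept nor that they are dropped.

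Two other sections bear on this. Under Section 7, "patients are randomized in a single-blinded fashion into one of 2 study arms"; who is blinded is not said. Section 16 describes how each patient learns the results: "contacted by the endoscopist either through the phone, mail, my chart or in person during a clinic visit to discuss endoscopic and pathology results".

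**The concern.** The primary endpoint is fixed by the colonoscopy and the pathology report that follows. Three of the four routes can be used after that point, and (c) arises during the procedure itself.

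The endoscopist works with or without the cuff and so cannot be blind to the arm. Because the endoscopist also discusses the pathology results with the patient, the discretion in (a) can be used by someone who knows both the arm and the SSA status. Whether the PI knows the arm is not stated.

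Route (b) is tied to the endpoint in another way. A suspicion of polyposis at colonoscopy rests on the polyps seen, and the trial asks whether the device shows more lesions.

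Route (c) is attributed to a baseline feature that randomisation should balance. Removal is optional, however, and so is decided case by case.

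Under (d) the loss is permanent. It includes the subject's complication data, although major complications are a listed secondary endpoint in Section 6.

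**Working it through.** **Inputs.** From the protocol: control SSADR 10%, effect 50%, stated power 0.809, 687 per arm (Section 8, sample-size paragraph); no allowance for withdrawals is stated. Assumed: the 50% is relative (10% against 15%), and the test is two-sided at 0.05, since neither point is stated. All removal scenarios are also assumed, because the protocol gives no withdrawal rate.

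**Method.** Two-proportion normal approximation with pooled variance under the null. With observed rates pC and pE, difference d = pE − pC and pooled rate p̄:

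- s0 = √[p̄(1 − p̄)(1/nC + 1/nE)]
- s1 = √[pC(1 − pC)/nC + pE(1 − pE)/nE]
- rejection probability = 1 − Φ((1.96·s0 − d)/s1) + Φ((−1.96·s0 − d)/s1)

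**The plan's own figure.** At 10% against 15%, n = 687: s0 = 0.01784, s1 = 0.01779, d = 0.05, so power is 0.801. The stated 0.809 is close enough to confirm this reading of the design.

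**Expected positives.** Control: 0.10 × 687 = 68.7. Cuff: 0.15 × 687 = 103.05 under the design effect, 68.7 under no effect. Removing k positives from an arm with x positives changes its rate to (x − k)/(687 − k). For example, seven removed from the cuff arm gives (103.05 − 7)/680 = 14.12%.

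**SSA-positive subjects removed, no true effect (10% in both arms)**

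| Removed | Control | Cuff | Type I error |
|---|---|---|---|
| 7 from each arm | 9.07% | 9.07% | 5.0% |
| 7 control, 3 cuff | 9.07% | 9.61% | 6.3% |
| 3 control only | 9.61% | 10.00% | 5.7% |
| 7 control only | 9.07% | 10.00% | 9.0% |

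**SSA-positive subjects removed, true 10% against 15%**

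| Removed | Control | Cuff | Power |
|---|---|---|---|
| None | 10.00% | 15.00% | 0.80 |
| 7 cuff, 4.67 control (in proportion to the rates) | 9.38% | 14.12% | 0.78 |
| 7 cuff, 3 control | 9.61% | 14.12% | 0.73 |
| 3 cuff only | 10.00% | 14.63% | 0.74 |
| 7 cuff only | 10.00% | 14.12% | 0.65 |

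**Less selective removal.** If seven subjects (1%) leave one arm and 30% of them are positive (2.1 subjects), type I error is 5.2% (control arm, no effect) or power is 0.78 (cuff arm, design effect).

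**Scope switch, 34 cuff subjects (5%) removed, no true effect.** If 3.4 are positive (10%), the cuff rate stays at 10.00% and type I error at 5.0%. If 1.7 are positive (5%), the rate is 10.26% and the error 5.3%. If none is positive, the rate is 68.7/653 = 10.52% and the error 6.2%.

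What drives the harm is imbalance between the arms in who is removed; the number removed matters much less.

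**The case against.** The strongest reply is that (a) to (c) rest on silence. Whether withdrawn subjects stay in the primary analysis is an analysis-set rule that a protocol commonly leaves to the SAP, and an SAP not shown here could keep them in their assigned arm. This stands as a limit, and it is why the bias is stated conditionally. It does not cover the permission itself, which is protocol text: an unblinded endoscopist may withdraw a subject from the research after the result is known. Nor does it cover (d), because no SAP can analyse discarded data.

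On (d), the choice is the subject's own. If the subject is the blinded party, the request cannot depend on a known arm, and participation lasts only one day. Selective loss of SSA-positive subjects by this route is therefore not obviously likely. The permanent loss of complication data remains.

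Section 11 can also be read so that the named circumstances explain the discretion, making (a) overlap with (b) and (c). That would narrow the open discretion, but withdrawal based on findings would still be there.

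Inflammatory bowel disease and a family history of hereditary polyposis syndromes are exclusion criteria in Section 4. Route (b) is then partly late recognition of people the trial meant to exclude, and such cases should be few. New IBD is not a polyp finding, so its link to SSADR is not shown. The polyposis part is still judged on the polyps found.

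Finally, the larger figures need removals that are both selective and one-sided. Seven control positives are about 10% of the 68.7 expected. No figure in the protocol supports that, and the balanced and proportional cases do little harm.

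**Conclusion.** The concern holds as a conditional risk and should be fixed. The withdrawal rules allow removal after the colonoscopy by a person who knows the arm, partly for reasons linked to the endpoint, and they order irrecoverable loss of data on a subject's request. If those removed leave the analysis, SSADR may be biased in either direction.

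The likely size is unknown. In the assumed scenarios it runs from nothing (balanced removal) to a type I error of 9.0% or a power of 0.65 (seven positives lost from one arm only). These figures rest on 687 per arm, 10% against 15%, and a two-sided 0.05 level. Confidence is medium, because an SAP could settle (a) to (c) and the frequency of withdrawal is not given.

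**What to change.** - State that every randomised subject who has a colonoscopy is analysed in the assigned arm for the primary endpoint, including those with suspected polyposis, new IBD or a scope switch. Limit any set that excludes them to a sensitivity analysis.
- State that withdrawal at the discretion of the endoscopist or PI does not remove data from the analysis.
- Record every withdrawal by arm, reason and timing: before or after the procedure, and before or after the pathology report.
- On a subject's request, stop further collection and keep the data already collected, including complications, as far as the consent allows.

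The cost is protocol wording, with the consent wording aligned to it; no extra subjects or procedures are needed. There are two drawbacks: a few scope-switch cases may slightly dilute the effect, and subjects must be told that data already collected may be kept.
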